8.3.1. Timing and Mechanism for Collecting Events

This table describes the timing, deadlines, and mechanism for collecting events.

Event	Collection Start	Collection Stop	Timing for Reporting to Sponsor or Designee	Mechanism for Reporting	Back-up Method of Reporting
Adverse Event					
AE	Signing of the ICF	Participation in study has ended	As soon as possible upon site awareness	AE CRF	N/A
Serious Adverse Event					
SAE and SAE updates – prior to start of study intervention and deemed reasonably possibly related to study procedures	Signing of ICF	Start of intervention	Immediately without exceeding 24 hrs	SAE CRF	SAE paper form
SAE ^a and SAE updates – after start of study intervention	Start of intervention	Participation in study has ended	Immediately without exceeding 24 hrs	SAE CRF	SAE paper form
SAE ^b – after participant's study participation has ended and the investigator becomes aware	After participant's study participation has ended	N/A	Promptly	SAE paper form	N/A
Pregnancy					
Pregnancy in female participants and female partners of male participants	After the start of study intervention	Until 1 month after the last dose of study intervention	Within 24 hrs (see Section 8.3.2)	Pregnancy paper form	Pregnancy paper form

Event	Collection Start	Collection Stop	Timing for Reporting to Sponsor or Designee	Mechanism for Reporting	Back-up Method of Reporting
Product Complaints					
PC associated with an SAE or might have led to an SAE	Start of study intervention	End of study intervention	Within 24 hrs of awareness	Product Complaint Form	N/A
PC not associated with an SAE	Start of study intervention	End of study intervention	Within 1 business day of awareness	Product Complaint Form	N/A
Updated PC information	—	—	As soon as possible upon site awareness	Originally completed Product Complaint Form with all changes signed and dated by the investigator	N/A
PC (if investigator becomes aware)	Participation in study has ended	N/A	Promptly	Product Complaint Form	

Abbreviations: AE = adverse event; CRF = case report form; ICF = informed consent form; N/A = not applicable; PC = product complaint; SAE = serious adverse event.

- a Death caused by disease progression should not be reported as an SAE.
- b Serious adverse events should not be reported unless the investigator deems them to be possibly related to study treatment or study participation.

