8.3.3.8. Major Adverse Cardiovascular Events

Deaths and nonfatal CV AEs will be adjudicated by a committee of physicians external to Lilly with cardiology expertise. The nonfatal CV AEs to be adjudicated include the following:

- myocardial infarction
- hospitalization for unstable angina
- hospitalization for heart failure
- coronary interventions, such as coronary artery bypass graft or percutaneous coronary intervention, and
- cerebrovascular events, including cerebrovascular accident (stroke) and transient ischemic attack.

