10.3.1. Definition of AE

AE Definition

- An AE is any untoward medical occurrence in a participant administered a pharmaceutical product and which does not necessarily have a causal relationship with the study intervention. An AE can therefore be any unfavorable and unintended sign (including an abnormal laboratory finding), symptom, or disease (new or exacerbated) temporally associated with the use of a medicinal (investigational) product, whether or not related to the medicinal (investigational) product.

Events Meeting the AE Definition

- Any abnormal laboratory test results (hematology, clinical chemistry, or urinalysis) or other safety assessments (for example, ECG, radiological scans, vital signs measurements), including those that worsen from baseline, considered clinically significant in the medical and scientific judgment of the investigator (that is, not related to progression of underlying disease).
- Exacerbation of a chronic or intermittent preexisting condition including either an increase in frequency and/or intensity of the condition.
- New condition detected or diagnosed after study intervention administration even though it may have been present before the start of the study.
- Signs, symptoms, or the clinical sequelae of a suspected drug-drug interaction.
- Medication error, misuse, or abuse of IMP, including signs, symptoms, or clinical sequelae.
- Lack of efficacy or failure of expected pharmacological action per se will not be reported as an AE or SAE. Such instances will be captured in the efficacy assessments. However, the signs, symptoms, and/or clinical sequelae resulting from lack of efficacy will be reported as AE or SAE if they fulfill the definition of an AE or SAE.

Events NOT Meeting the AE Definition

- Any clinically significant abnormal laboratory findings or other abnormal safety assessments that are associated with the underlying disease, unless judged by the investigator to be more severe than expected for the participant's condition.
- The disease or disorder being studied or expected progression, signs, or symptoms of the disease or disorder being studied, unless more severe than expected for the participant's condition.

- Medical or surgical procedure (for example, endoscopy, appendectomy): the condition that leads to the procedure is the AE.
- Situations in which an untoward medical occurrence did not occur (social and/or convenience admission to a hospital).

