10.3.2. Definition of SAE

An SAE is defined as any untoward medical occurrence that, at any dose, meets one or more of the criteria listed:

a. Results in death

b. Is life-threatening

The term *life-threatening* in the definition of *serious* refers to an event in which the participant was at risk of death at the time of the event. It does not refer to an event, which hypothetically might have caused death, if it were more severe.

c. Requires inpatient hospitalization or prolongation of existing hospitalization

- In general, hospitalization signifies that the participant has been admitted to hospital or emergency ward (usually involving at least an overnight stay) for observation and/or treatment that would not have been appropriate in the physician's office or outpatient setting. Complications that occur during hospitalization are AEs. If a complication prolongs hospitalization or fulfills any other serious criteria, the event is serious. When in doubt as to whether hospitalization occurred or was necessary, the AE should be considered serious.
- Hospitalization for elective treatment of a preexisting condition that did not worsen from baseline is not considered an AE.

d. Results in persistent disability or incapacity

- The term disability means a substantial disruption of a person's ability to conduct normal life functions.
- This definition is not intended to include experiences of relatively minor medical significance such as uncomplicated headache, nausea, vomiting, diarrhea, influenza, and accidental trauma (for example, sprained ankle) which may interfere with or prevent everyday life functions but do not constitute a substantial disruption.

e. Is a congenital anomaly or birth defect

- Abnormal pregnancy outcomes (for example, spontaneous abortion, fetal death, stillbirth, congenital anomalies, ectopic pregnancy) are considered SAEs.

f. Other situations

- Medical or scientific judgment should be exercised by the investigator in deciding whether SAE reporting is appropriate in other situations such as important medical events that may not be immediately life-threatening or result in death or hospitalization but may jeopardize the participant or may require medical or surgical intervention to prevent one of the other outcomes listed in the above definition. These events should usually be considered serious.

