#### **4.6.1.2. Serious Adverse Events**

The number and percentage of patients who experienced an SAE (including deaths and SAEs temporally associated or preceding deaths) will be summarized by treatment using MedDRA PT nested within SOC. Events will be ordered by decreasing frequency within SOC. A listing of all SAEs will be provided. Listing will include but not limited to treatment, patient ID including the site number, treatment group, date of event, age at the time of enrollment, gender, MedDRA SOC and PT, severity, action taken, outcome, relationship to study drug, time from first dose of study drug to the event, and event duration.

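### Footnote a of protocol Section 8.3.1 exempts deaths from an undefined disease progression from SAE reporting, in conflict with the protocol's own SAE definition and the SAP's SAE table

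*Protocol*

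**What the plan says.** The timing table in protocol Section 8.3.1 gives different deadlines by event type. An SAE after the start of study intervention goes to the sponsor "Immediately without exceeding 24 hrs". An event that is only an AE goes "As soon as possible upon site awareness". Footnote a is attached to that SAE row and reads "Death caused by disease progression should not be reported as an SAE".

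Appendix 3 gives the definitions. Section 10.3.2 states: "An SAE is defined as any untoward medical occurrence that, at any dose, meets one or more of the criteria listed". The first criterion is "Results in death", and no exception for disease progression follows it. Section 10.3.1 lists, among events that are not AEs, the disease under study or its "expected progression, signs, or symptoms of the disease or disorder being studied, unless more severe than expected" for that participant. It also makes the clinical consequences of lack of efficacy reportable when they meet the AE or SAE definition.

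Other text deals with deaths directly. Protocol Section 8.3.3.8 says: "Deaths and nonfatal CV AEs will be adjudicated by a committee of physicians external to Lilly with cardiology expertise". The SAE summary in SAP Section 4.6.1.2 is worded "The number and percentage of patients who experienced an SAE (including deaths and SAEs temporally associated or preceding deaths", with the bracket closing there. SAP Section 4.6.1.1 plans a listing of every death, and SAP Section 4.6.1 plans narratives for deaths.

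**The concern.** The footnote is a direct instruction to sites, placed in the table that they use to decide what to send and how fast. It points the opposite way from the SAE definition in the same protocol. Its key term has no definition in a type 2 diabetes trial, where a fatal cardiovascular, renal or hyperglycaemic complication could be read as progression of the underlying disease.

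The judgement about cause also comes before the decision to report. The SAE definition in Section 10.3.2 does not depend on cause.

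Two things are at stake: whether a death reaches the sponsor within 24 hours, and whether the SAE table and the registry SAE output agree with the count of deaths. Timeliness matters here because the trial is open-label with no data monitoring committee, and because protocol Section 10.3.6 treats prompt SAE notification as essential to the sponsor's legal and ethical duties.

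**Working it through.** No figure in the plan needs to be reproduced, because the point is textual. The check sets the rules side by side and then asks what depends on SAE status.

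**Step 1. Apply both rules to the kinds of death a site might call disease progression.**

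| Type of death | Appendix 3 (Sections 10.3.1 and 10.3.2) | Footnote a | Agreement |
|---|---|---|---|
| Expected progression, no more severe than expected | Arguably not an AE, so not an SAE | Not an SAE | Consistent on that reading |
| Progression more severe than expected | AE, and an SAE because it ends in death | Not an SAE | Contradiction |
| Consequence of lack of efficacy, labelled progression by the site | Reportable if it meets the AE or SAE definition, which a fatal event does | Not an SAE | Contradiction |
| Complication that was life-threatening or needed admission before death | SAE on other criteria as well | Covers only the death | The preceding event is still reportable |

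The footnote and Appendix 3 agree only in the first row, and only if a death can count as no more severe than expected. The second and third rows are real conflicts, because the footnote has no severity condition and makes no allowance for lack of efficacy.

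**Step 2. What depends on SAE status.**

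- *Deadline.* In the Section 8.3.1 table, apart from pregnancy and product complaints, the SAE rows are the only ones with a 24-hour limit. The AE row has no hour limit. Section 10.3.4 asks for post-mortem findings when a participant dies, but sets no deadline.
- *SAE table.* SAP Section 4.6.1.2 summarizes SAEs by preferred term within system organ class. A death never filed as an SAE may leave no record for that table, although the table is described as including deaths.
- *Registry output.* SAP Section 6.4 gives total deaths, and deaths causally related to treatment, for each SAE. A death with no SAE record has no term under which to be counted.

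**Step 3. What is not stated to depend on SAE status.**

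- Deaths are summarized from first dose to the end of safety follow-up (protocol Section 9.3.5, SAP Section 4.6).
- Deaths have narratives (SAP Section 4.6.1).
- All deaths are listed, with the investigator's cause and the adjudicated cause (SAP Section 4.6.1.1).
- Deaths are adjudicated (protocol Section 8.3.3.8).

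**Step 4. Scale.** About 250 participants are randomized 1:1, so 250/2 = 125 per arm. One death missing from the SAE table changes that arm's SAE incidence by 1/125 = 0.8 percentage points, provided the participant had no other SAE. Neither document gives a mortality rate or the fraction of deaths a site might call progression, so the number of affected deaths cannot be estimated.

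**The case against.** The strongest defence is Section 10.3.1. If expected progression of the studied disease is not an AE, it cannot be an SAE, and the footnote only applies that rule to deaths. This explains where the footnote may come from, but it does not remove the conflict. The exclusion in Section 10.3.1 depends on severity, and the footnote does not.

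The second defence is that the plan already treats the likely fatal complications as safety outcomes. Myocardial infarction, stroke and hospitalization for heart failure are adjudicated. Renal safety and severe, persistent hyperglycemia are safety topics of special interest. Many fatal complications would meet the life-threatening or hospitalization criterion before death. This stands, and it narrows the exposed case to a death with no earlier reportable serious event that the site labels progression of diabetes.

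The third defence is that deaths are captured by several routes outside SAE reporting. This also stands. A reader might infer from the footnote that a death could disappear from the trial results. The documents do not support that: the summary, narratives, listing and adjudication all cover deaths, and none is stated to require an SAE report.

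**Conclusion.** The contradiction is real and is in current text. An unconditional exemption for an undefined category of death conflicts with Section 10.3.2, omits the severity condition of Section 10.3.1, and does not fit the SAE summary in SAP Section 4.6.1.2. The consequence is limited. A site following the footnote could miss the 24-hour deadline, and the death could be absent from the SAE table and the registry SAE output while appearing in the death listing. This rests on a site applying the footnote as written to a death that no other SAE criterion has already captured.

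Two further inferences are tempting but unsupported. Because the trial is open-label, a reader might suppose that the exemption would be used differently in the two arms. Neither document gives a mechanism for this, and the adjudication committee is blinded to treatment (protocol Section 10.1.5). A reader might also suppose that adjudication fails as a backstop because it sees only what is filed as an SAE. No section says that deaths reach the committee only through SAE forms, and the footnote restricts SAE reporting alone.

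**What to change.** Delete footnote a from the table in protocol Section 8.3.1. Deaths after the start of study intervention then follow the Section 10.3.2 definition and the 24-hour SAE route, and the SAP's SAE and registry outputs match the text that describes them.

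If the sponsor wants to keep an exemption, the minimum is to define disease progression for this trial, carry over the severity condition of Section 10.3.1, and reconcile the result with Section 10.3.2 and SAP Sections 4.6.1.2 and 6.4.

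Deletion costs one line in a protocol amendment and a reminder in site training. No visit, sample size or analysis model changes.

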8.3.2. Pregnancy

Collection of pregnancy information

Male participants with partners who become pregnant

The investigator will attempt to collect pregnancy information on any male participant's female partner who becomes pregnant while the male participant is in this study. This applies only to male participants who receive study intervention.

After learning of a pregnancy in the female partner of a study participant, the investigator will

- obtain a consent to release information from the pregnant female partner directly, and
- within 24 hours after obtaining this consent will record pregnancy information on the appropriate form and submit it to the sponsor.

The female partner will also be followed to determine the outcome of the pregnancy. Information on the status of the mother and child will be forwarded to the sponsor. Generally, the follow-up will be no longer than 6 to 8 weeks following the estimated delivery date. Any termination of the pregnancy will be reported regardless of gestational age, fetal status (presence or absence of anomalies), or indication for the procedure.

Female participants who become pregnant

The investigator will collect pregnancy information on any female participant who becomes pregnant while participating in this study. The initial information will be recorded on the appropriate form and submitted to the sponsor within 24 hours of learning of a participant's pregnancy.

The participant will be followed to determine the outcome of the pregnancy. The investigator will collect follow-up information on the participant and the neonate, and the information will be forwarded to the sponsor. Generally, follow-up will not be required for longer than 6 to 8 weeks beyond the estimated delivery date. Any termination of pregnancy will be reported, regardless of gestational age, fetal status (presence or absence of anomalies), or indication for the procedure.

While pregnancy itself is not considered to be an AE or SAE, any pregnancy complication or elective termination of a pregnancy for medical reasons will be reported as an AE or SAE.

A spontaneous abortion (occurring at <20 weeks' gestational age) or still birth (occurring at ≥20 weeks' gestational age) is always considered to be an SAE and will be reported as such.

Any poststudy pregnancy-related SAE considered reasonably related to the study intervention by the investigator will be reported to the sponsor as described in protocol Section 8.3.1. While the investigator is not obligated to actively seek this information in former study participants, he or she may learn of an SAE through spontaneous reporting.

Any female participant who becomes pregnant while participating in the study will be withdrawn from the study. If the participant is discontinued from the study, follow the standard discontinuation process and continue directly to the follow-up phase. The follow-up on the pregnancy outcome should continue independent of intervention or study discontinuation.

8.3.3. Safety Topics of Special Interest

The safety topics of special interest are

- gastrointestinal (Section 8.3.3.1)
- dehydration (Section 8.3.3.2)
- renal safety (Section 8.3.3.3)
- exocrine pancreas safety (Section 8.3.3.4)
- thyroid C-cell hyperplasia and C-cell neoplasms (Section 8.3.3.5)
- hypoglycemia (Section 8.3.3.6)
- severe, persistent hyperglycemia (Section 8.3.3.7)
- major adverse cardiovascular event (MACE) (Section 8.3.3.8)
- arrhythmias and cardiac conduction disorders (Section 8.3.3.9)
- hypersensitivity reactions (Section 8.3.3.10)
- injection-site reactions (Section 8.3.3.11)

- diabetic retinopathy complications (Section 8.3.3.12), and
- hepatobiliary disorders (Section 8.3.3.13).

8.3.3.1. Gastrointestinal Adverse Event

Tirzepatide may cause severe GI AEs, such as nausea, vomiting, and diarrhea. Information about severe GI AEs as well as anti-emetic/anti-diarrheal use will be collected in the CRF/AE form.

For detailed information concerning the management of GI AEs, refer to Section 6.5.1.

8.3.3.2. Dehydration

Severe gastrointestinal events may lead to dehydration and volume depletion, which can cause a deterioration in renal function, including acute renal failure. Many of the reported adverse renal events occurred in participants who had experienced nausea, vomiting, diarrhea, or dehydration. Participants should be advised of the potential risk of dehydration, particularly in relation to gastrointestinal adverse reactions or other AEs and take precautions to avoid fluid depletion.

8.3.3.3. Renal Safety

Renal safety will be assessed based on repeated renal functional assessment as well as assessment of AEs suggestive of acute or worsening of chronic renal disease.

8.3.3.4. Exocrine Pancreas Safety

Diagnosis of acute pancreatitis

The diagnosis of acute pancreatitis requires 2 of the following 3 features (Banks 2006; Kouzumi 2006):

- abdominal pain, characteristic of acute pancreatitis, that is, epigastric pain radiating to the back, often associated with nausea and vomiting
- serum amylase (total, pancreatic, or both) and/or lipase $\geq 3x$ ULN, and
- characteristic findings of acute pancreatitis on CT scan or MRI.

If acute pancreatitis is suspected, the investigator should

- obtain appropriate laboratory tests, including pancreatic amylase and lipase, via the central laboratory and, if needed, via a local laboratory as well, and
- perform imaging studies, such as abdominal CT scan with or without contrast, MRI, or gallbladder ultrasound.

Discontinuation and rescue intervention for acute pancreatitis

If laboratory values and/or abdominal imaging support the diagnosis of acute pancreatitis, the participant must discontinue therapy with investigational product(s) but will continue in the study on another glucose-lowering regimen (details on rescue intervention will be provided). The most appropriate diabetes therapeutic regimen will be decided by the investigator, based on the participant's clinical status. A review of the participant's concomitant medications should be conducted to assess any potential causal relationship with pancreatitis.

Reporting adverse events and serious adverse events of acute pancreatitis

Each event of pancreatitis must be reported as an AE or SAE.

The investigator must report the event as an SAE if the typical signs and/or symptoms of pancreatitis

- 1) are present, and
- 2) are confirmed by
 - a) laboratory values (lipase or amylase [total and/or pancreatic]), and
 - b) imaging studies.

If a potential event does not meet all of these criteria, the investigator will decide the seriousness of the event, either AE or SAE.

The investigator will also review the participant's concomitant medications to assess any potential causal relationship with pancreatitis and will report the relatedness of study intervention(s) to the event.

Pancreatic hyperenzymemia

Each participant will have measurements of pancreatic amylase and lipase, assessed at the central laboratory, as shown in Section 1.3 to assess the effects of the investigational doses of study intervention on pancreatic enzyme levels.

Serial measures of pancreatic enzymes have limited clinical value for predicting episodes of acute pancreatitis in asymptomatic participants (Koizumi 2006; Steinberg 2017 a, 2017b). Thus, further diagnostic follow-up of cases of asymptomatic pancreatic hyperenzymemia, lipase and/or pancreatic amylase 3x ULN or more is not mandated but may be performed based on the investigator's clinical judgment and assessment of the participant's overall clinical condition.

Only cases of pancreatic hyperenzymemia that undergo additional diagnostic follow-up and/or are accompanied by symptoms suggestive of pancreatitis will be submitted for adjudication.

Case adjudication and data entry

An independent clinical endpoint committee will adjudicate all suspected cases of acute or chronic pancreatitis. The adjudication committee will also receive data on AEs of severe or serious abdominal pain of unknown etiology to assess for possible pancreatitis or other pancreatic disease.

Study site staff will enter relevant data for participants with acute or chronic pancreatitis or those with AEs of severe or serious abdominal pain into a specifically designed CRF page. The adjudication committee representative will enter the results of adjudication into a corresponding CRF page.

